1.2. Sample Size Considerations

A sample size of 184 subjects per group (total, 368 subjects) will provide at least 90% power to detect a change in the primary outcome measure (change from baseline in "on" time without troublesome dyskinesia) of 1 hour with a standard deviation of 2.5, a 2 sided alpha level = 0.049, and assuming a 27% dropout rate. The sample size calculation was based on a two-sample t-test with equal variance.

Given that the assumptions for the sample size were based on a preliminary study of limited sample size using a different dosing schedule, it is unknown if the assumption of a standard deviation of 2.5 is a reasonable estimate of the population variability and appropriate for this study as designed. To this end, an interim analysis of the primary efficacy endpoint will be included to assess the adequacy of the overall sample size relative to achieving the study objectives. [Section 9.1](#) provides further detail on the conduct of the interim analysis. Should the interim analysis indicate a requirement of sample size increase per pre-defined decision rule ([Section 9.1](#)) to maintain statistical power, Cerevel will extend enrollment to achieve the required sample size.

In the event of higher than anticipated early terminations due to COVID-19 or other reasons, Cerevel may also extend enrollment in order to maintain the planned statistical power.

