5.2. Populations for Analyses

The analysis populations are defined [Table 4](#).

Table 4: Populations for Analysis

Population	Description	Analysis
ITT	All randomized subjects	Demographic and Baseline Characteristics
FAS	All randomized subjects who receive at least 1 dose of IMP. This will be the safety analysis set.	Safety analysis
mITT	All randomized subjects who receive at least 1 dose of IMP and have both a valid baseline and at least 1 postbaseline valid Hauser diary entry	Primary analysis set for efficacy
Endpoint completers	All subjects in the mITT population who complete a valid Hauser diary at endpoint	Sensitivity analysis for efficacy
PK Analysis Set	All randomized subjects who receive at least 1 dose of IMP and have at least 1 measurable tavapadon (CVL-751) concentration	PK analysis

Abbreviations: FAS = full analysis set, IMP = investigational medicinal product, ITT = intent-to-treat, mITT = modified intent-to-treat, PK = pharmacokinetic.

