5.9.3.3. Impact of Missing Values Handling

Whilst every effort will be made to prevent avoidable missing values during the study conduct ([National Research Council, 2010](#)), it is unrealistic to expect no missing values in clinical trials. The impact of missing values on the analysis results will be assessed by the sensitivity analyses described below.

Under Missing at Random (MAR) Assumption

Multiple imputation (MI) will be performed to replace each missing value with a set of plausible values that represent the uncertainty about the correct value to impute. The Markov chain (MCMC) method will be utilized for the mITT set. SAS PROC MI will be used to generate 27 possible imputed datasets: Each of these datasets will be analyzed using PROC MIXED in SAS using the MMRM model as described in [Section 5.9.2](#). The results of the analyses of the datasets will be combined using PROC MIANALYZE to produce an inferential result.

Considerations of Data Potentially Missing Not at Random (MNAR)

A pattern mixture model (PMM) approach will be used to address potentially MNAR patterns. The following three patterns of subjects in the mITT set will be considered:

- 1) Subjects with no missing values from discontinuation or from initiation of prohibited Parkinson's disease concomitant mediation during treatment period.
- 2) Subjects with missing values from the types of ICEs below will be considered having MNAR
 - a. Subjects who discontinue due to reasons, as recorded on the eCRF, of lack of efficacy, adverse events associated with motor symptoms of Parkinson's disease, physician decision, and withdrawal by subject.
 - b. Subjects who initiated concomitant Parkinson's disease medications (ATC classifications of ADAMANTANE DERIVATIVES, OTHER DOPAMINERGIC AGENTS, OTHER ANTIPARKINSON DRUGS, MONOAMINE OXIDASE B INHIBITORS, or ANTICHOLINESTERASES) after the first dose of IMP and prior to the last dose of IMP with a use duration of 7 days or more will be considered having a potential confounding ICE. The efficacy data post ICE will be treated as missing with the missing pattern of MNAR.

The MNAR cases will be identified and documented prior to database lock and unblinding ([Section 9.6](#)).

- 3) Subjects with missing values from the type of ICEs below will be considered as having MAR

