 - a. Missing values after discontinuation due to reasons, as recorded on the eCRF, of death, pregnancy, loss to follow-up, adverse event unrelated to motor symptoms of Parkinson's disease, non-compliance, site termination, protocol deviation, failure to meet continuation criteria and other will be considered as MAR.

The MNAR pattern 2) above in the active treatment group will be imputed using the jump to reference (J2R) method (Cro et. al. 2020) by assuming that patients jump to behave like those in the placebo group following their last observed time point. However, such MNAR in the placebo group will still be imputed as MAR using the standard multiple imputation method.

The MAR patterns 3) will be imputed using the standard multiple imputation method described above.

Other missing values due to missed visits/assessments before endpoint or discontinuation will also be assumed as MAR and imputed using the standard multiple imputation method for all three patterns.

Core codes for MAR and MNAR imputations are provided in [Section 9.7](#).

Under Missing Completely at Random (MCAR) Assumption

An additional sensitivity analysis will be conducted on the Endpoint (Week 26) Completer set using the MMRM analysis method described in [Section 5.9.2](#).

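### The imputation and jump-to-reference sensitivity analyses are confined to mITT, so tavapadon subjects who stop before any valid post-baseline diary for a jump-to-reference reason are dropped instead of being set to placebo behaviour

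*SAP*

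**What the plan says.** SAP 5.9.3.3 plans two imputation analyses to test how missing values are handled. For multiple imputation under missing at random (MAR), the MCMC "method will be utilized for the mITT set". For data possibly missing not at random (MNAR), "The following three patterns of subjects in the mITT set will be considered". Table 4 in SAP 5.2 admits to mITT only dosed subjects who "have both a valid baseline and at least 1 postbaseline valid Hauser diary entry".

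In the pattern-mixture analysis, tavapadon subjects in the MNAR pattern are imputed by jump-to-reference (J2R), "by assuming that patients jump to behave like those in the placebo group following their last observed time point". Placebo subjects in that pattern are imputed under MAR. The MNAR pattern covers four reasons for stopping (lack of efficacy, motor-symptom adverse event, physician decision, withdrawal by subject) and the start of a Parkinson's medication used for at least 7 days. Other reasons for stopping, including adverse events unrelated to motor symptoms, are MAR.

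Table 4 assigns ITT to demographics and baseline, SAP 5.6 adds disposition, and FAS is for safety. SAP 5.10.3 carries the same sensitivity analyses over to the key secondary endpoint.

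**The concern.** Membership of mITT depends on something that happens after randomisation: returning a valid diary, first scheduled for the end of Week 2. The MMRM loses little by this, because a subject with no post-baseline value contributes nothing to a model of change from baseline.

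Imputation is different. A subject with only a baseline diary can be imputed, and the value imputed should depend on why the subject stopped. Under the mITT restriction it also depends on whether a diary came back. SAP 5.9.1 already treats discontinuation as an intercurrent event to be handled by a strategy, yet the population definition removes some of the same discontinuations.

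At stake is the one planned analysis that departs from MAR against the drug. If it omits tavapadon subjects whom its own rule would set to placebo behaviour, its estimate comes out too high whenever the drug has a positive effect.

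**Working it through.** **1. The plan's design figure.** SAP 1.2 states: "A sample size of 184 subjects per group (total, 368 subjects) will provide at least 90% power" for an effect "of 1 hour with a standard deviation of 2.5", with "2 sided alpha level = 0.049, and assuming a 27% dropout rate". It adds: "The sample size calculation was based on a two-sample t-test with equal variance".
- Evaluable per arm: 2 × [2.5 × (z for 0.049 two-sided + z for 90% power)]² / 1² = 132.04, so 133.
- Randomised per arm: 133 / 0.73 = 182.2, so 183, against 184 stated.
- A two-sample t-test with 135 completers per arm (the 270 of SAP Table 5) has 90.4% power, which matches Table 5.

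The design figure reproduces. It does not decide this point, which turns on the analysis sets.

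**2. Set used by each analysis of the primary endpoint.**

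| Analysis | SAP section | Set |
|---|---|---|
| Primary MMRM | 5.9.1, 5.11 | mITT |
| Final dose level | 5.9.3.1 | mITT |
| Actual treatment (conditional) | 5.9.3.2 | none named; uses the 5.9.2 MMRM |
| Multiple imputation, MAR | 5.9.3.3 | mITT |
| Pattern mixture with J2R | 5.9.3.3 | mITT |
| Endpoint completers | 5.9.3.3, Table 4 | subset of mITT |
| Subgroups | 5.9.4 | mITT |

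The actual-treatment analysis cannot use a subject without a post-baseline value either. No analysis of this endpoint therefore includes a subject who has no valid post-baseline diary.

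**3. Is the restriction technically needed?** It does not appear so. The PROC MI code in SAP 9.7.1 lists baseline (y0) with the visits, and the J2R macro call in SAP 9.7.2 uses BASE as a covariate.

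**4. Which excluded subjects would move the estimate?**
- Tavapadon, MAR reason: imputed at about the tavapadon mean, so almost no change.
- Placebo, any reason: imputed under MAR at about the placebo mean, so almost no change.
- Tavapadon, J2R reason: imputed at the placebo mean, so they contribute a difference of zero.

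**5. Size.** Let D be the J2R difference on mITT and x the share of the tavapadon arm in the third group. On all randomised subjects with a valid baseline diary the difference is about (1 − x) × D, so the mITT figure is too high by x × D. With D = 1 h:

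| x (assumed) | Tavapadon subjects (184 × x) | Difference | Overstatement |
|---|---|---|---|
| 1% | 1.8 | 0.99 h | 0.01 h |
| 2% | 3.7 | 0.98 h | 0.02 h |
| 5% | 9.2 | 0.95 h | 0.05 h |

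**6. What x might be.** The documents give no early-dropout rate. If the 27% were spread evenly over the 189 treatment days, the share before Day 14 would be 27% × 14/189 = 2.0%, or about 7 of 368 subjects, both arms and all reasons together. The part that is tavapadon, J2R reason and without a diary would be smaller, unless dropout is concentrated in the first weeks.

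**The case against.** Three stronger readings are tempting, and the documents do not support them.

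*All of the earliest dropouts are lost.* The Week 27 assessments, diary collection included, are required at early termination (SAP Table 7, note b). Those data are mapped by study day, and the Week 2 window is Days 2 to 24 (SAP 4.2). A subject who stops before Week 2 and returns a valid diary enters mITT. Values after discontinuation are censored, so such a subject may still have nothing usable.

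*Early tolerability stops in the active arm bias the J2R result.* Protocol 2.3 links nausea, orthostatic changes and fatigue to titration speed, but it gives no timing for discontinuations, and the titration rows of the dosing table are redacted. More to the point, the SAP treats stops for non-motor adverse events as MAR, so adding those subjects back would give essentially no J2R dilution.

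*Robustness is shown to be overstated.* It is not, because x is unknown. Against a design standard error of 2.5 × √(2/135) = 0.30 h, a shift of 0.02 h is small. An x of 10% would need about 18 of the 184 tavapadon subjects, over a third of that arm's roughly 50 expected dropouts (184 × 0.27), to stop that early for J2R reasons without a valid diary.

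It can also be argued that mITT is the declared estimand population and the protocol's primary efficacy set, so these analyses rightly hold the population fixed while the missing-data assumption varies. SAP 5.6 also reports disposition on ITT and the size of each set. That is a fair defence of mITT for the MMRM. It does not explain why an analysis of missing data should leave out subjects with no post-baseline data when the models can take them, or why the J2R rule should apply only if a diary was returned.

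**Conclusion.** The point holds in a limited form. Subjects with no valid post-baseline diary are outside every planned analysis of the primary endpoint. In the J2R analysis this removes tavapadon subjects whom the SAP's own rule would set to placebo behaviour. For that group the direction follows from the rule: with a positive effect, leaving them out can only raise the J2R estimate. The size does not follow. It is about x h per 1 h of effect, so 0.01 to 0.05 h for assumed shares of 1 to 5%, and even dropout suggests the lower end. The approximation takes MAR additions to fall at their arm means and J2R additions at the placebo mean. Sample size and the primary MMRM are unaffected. This is a modest, inexpensive improvement to a sensitivity analysis.

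**What to change.** In SAP 5.9.3.3, and so in 5.10.3 by reference:

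- Run the multiple-imputation and pattern-mixture analyses on all randomised subjects with a valid baseline diary, and leave the pattern rules as they are. Eligibility already requires a completed screening diary, so this should be close to ITT.
- Add one sentence stating that J2R starts from baseline when a subject has no usable post-baseline value. As written, the rule starts from the last observed time point and does not cover this case, which can arise even within mITT when early-termination values are censored.
- Keep mITT for the primary MMRM.

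Protocol 9.4.1 calls for sensitivity analyses under different missing-data mechanisms without tying them to mITT, so a protocol amendment appears unnecessary. The cost is a change of input dataset and a small programming check that the external J2R macros accept subjects with baseline only. The downside is a sensitivity estimate that may be slightly less favourable.

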5.9.4. Subgroup Analyses

Subgroup analyses of the primary endpoint will be made based on the mITT set to assess consistency of the intervention effect across the following subgroups:

- Age group: < 65 vs \geq 65 years
- Sex: female vs male
- Hoehn and Yahr Status at screening: stage 2, 2.5, or 3 in the “on” state.
- Baseline daily “on” time without troublesome dyskinesia: \leq baseline median vs $>$ baseline median (median of the mITT set regardless treatment group)
- Baseline daily “off” time: \leq baseline median vs $>$ baseline median (median of the mITT set regardless treatment group)
- Race: white vs others
- Region: United State vs Non-US

If the number of subjects within a subgroup is too small (less than 10% of the mITT set), the subgroup categories may be redefined or excluded prior to unblinding the study. Provided that the sample sizes in the subgroups allow, the MMRM analysis method described in [Section 5.9.2](#) will be applied to the subgroup analysis. The treatment effect across subgroups will be summarized by forest plots.

5.10. Key Secondary Efficacy Analyses

5.10.1. Secondary Estimand

The key research question for the first secondary efficacy variable will be addressed with an estimand based on the following attributes:

- 1) Treatments: treatments as randomized regardless of the actual treatment received.
- 2) Target study population of interest: subjects in the modified intent-to-treat (mITT) population.
- 3) Endpoint (variable) of interest: change from baseline to Week 26 in total daily “off” time based on the 2 day average of the self completed home diary.
- 4) Population level summary of interest: estimated mean difference between tavapadon group and placebo group in the endpoint of interest.
- 5) Strategy for Intercurrent events (ICEs): a hypothetical strategy will be used to address intercurrent events (ICEs) of potential death, treatment discontinuations, missed visits/assessments, and start of prohibited concomitant Parkinson’s disease medications. The data after treatment discontinuations or after the start of prohibited concomitant Parkinson’s disease treatments will be censored under the hypothetical strategy.

5.10.2. Main Analytical Approach

Similar to the analysis of the primary efficacy variable, the change from baseline to each study visit in total daily “off” time based on the 2 day average of the self-completed home diary prior to each visit will be summarized by visit and treatment group. A mixed model repeated measures (MMRM) analysis will be used with fixed effect of treatment group, visits, and interaction between treatment group and visit. The baseline value of total daily “off” time (based on the 2 day average prior to the baseline visit) will be included as a covariate. Subject will be included as a random effect. An unstructured covariance structure will be used for the repeated measures. If the unstructured covariance matrix results in convergence issue, the heterogeneous Toeplitz covariance structure followed by the heterogeneous first-order autoregressive (AR(1)) structure will be used. The Kenward-Roger approximation will be used to estimate the denominator degrees of freedom. The difference between tavapadon and placebo at the endpoint visit will be estimated based on the Least Squares Mean (LSMean) difference between the treatment groups at the endpoint visit from the MMRM with the associated 95% confidence intervals (CI) and P-values. The missing values are assumed to be missing at random for the main analysis, including missing due to missed visits or early termination due to COVID-19 control measures. Time curve plots will be presented for both raw Mean (SEM) and LSMean (SE).

5.10.3. Sensitivity Analyses

The sensitivity analyses described in [Section 5.9.3](#) for the primary estimand will also be performed for the key secondary efficacy estimand.

5.10.4. Subgroup Analyses

The subgroup analyses described in [Section 5.9.4](#) for the primary estimand will also be performed for the key secondary efficacy estimand.

5.11. Summary of Primary and Key Secondary Efficacy Analyses

ICE Strategy	Primary Analysis	Sensitivity Analysis	Subgroup Analysis
Primary Endpoint: Change from Baseline to Week 26 in daily “on” time without troublesome dyskinesia based on the 2-day average of the self-completed home diary for motor function status (Hauser diary).			
Hypothetical strategy with data after treatment discontinuations or after the start of prohibited concomitant medications censored	
 ■ mITT population ■ Treatment as randomized ■ MMRM described in Section 5.9.2 	
 ■ Treatment effect at final dose levels ■ Treatment effect based on actual treatment received, if applicable ■ Missing values imputation using multiple imputations (MI) ■ Missing values imputation using pattern mixture model (PMM) ■ Endpoint completer analysis 	
 ■ Age ■ Sex ■ Hoehn&Yahr Status ■ Baseline daily “on” time without dyskinesia ■ Baseline daily “off” time ■ Race ■ Region
Key Secondary Endpoint: Change from Baseline to Week 26 in daily “off” time on the 2-day average of the self-completed home diary for motor function status (Hauser diary).			
Hypothetical strategy with data after treatment discontinuations or after the start of prohibited concomitant medications censored	
 ■ mITT population ■ Treatment as randomized ■ MMRM described in Section 5.9.2 	
 ■ Treatment effect at final dose levels ■ Treatment effect based on actual treatment received, if applicable ■ Missing values imputation using multiple imputations (MI) ■ Missing values imputation using pattern mixture model (PMM) ■ Endpoint completer analysis 	
 ■ Age ■ Sex ■ Hoehn&Yahr Status ■ Baseline daily “on” time without dyskinesia ■ Baseline daily “off” time ■ Race ■ Region

5.12. Other Secondary Efficacy Analyses

Endpoint	Analysis Population	ICE Strategy	Analysis Method
Change from baseline at each visit in total “on” time without troublesome dyskinesia based on the 2 day average of the self-completed motor home diary (all time points)	mITT	Hypothetical	MMRM described in Section 5.9.2
Change from baseline at each visit in total “off” time based on the 2 day average of the self-completed motor home diary (all time points)	mITT	Hypothetical	MMRM described in Section 5.9.2
Change from baseline in the MDS UPDRS Part I score (all time points)	mITT	Hypothetical	MMRM described in Section 5.9.2
Change from baseline in the MDS UPDRS Part II score (all time points)	mITT	Hypothetical	MMRM described in Section 5.9.2
Change from baseline in the MDS UPDRS Part III score (all time points)	mITT	Hypothetical	MMRM described in Section 5.9.2
Change from baseline in the PDQ 39 score	mITT	Hypothetical	MMRM described in Section 5.9.2
Change from baseline in the EQ-5D-5L index score	mITT	Hypothetical	MMRM described in Section 5.9.2
Change from baseline in EQ-5D-5L VAS score	mITT	Hypothetical	MMRM described in Section 5.9.2

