9.3 Populations for Analyses

The analysis populations are defined ([Table 8](#)).

Table 8 Populations for Analysis

Population	Description	Analysis
ITT	All randomized subjects	Demographic and Baseline Characteristics
FAS	All randomized subjects who receive at least 1 dose of IMP. This will be the safety analysis set.	Safety analysis
mITT	All randomized subjects who receive at least 1 dose of IMP and have both a baseline and at least 1 postbaseline Hauser diary entry	Primary analysis set for efficacy
Endpoint completers	All subjects in the mITT population who complete the Hauser diary at endpoint	Sensitivity analysis for efficacy
PK Analysis Set	All randomized subjects who receive at least 1 dose of IMP and have at least 1 measurable tavapadon (CVL-751) concentration	PK analysis

Abbreviations: FAS = full analysis set, IMP = investigational medicinal product, ITT = intent-to-treat, mITT = modified intent-to-treat, PK = pharmacokinetic.

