Secondary and Other	
Continuous secondary and other endpoints (MDS-UPDRS, EQ-5D-5L index and VAS scores and PDQ-39 score) will be analyzed in a manner similar to that used for the primary and key secondary efficacy endpoints. Categorical endpoints will be analyzed on the mITT population using the SAS® GLIMMIX procedure for binomial data with logit link. This generalized linear mixed model analysis will include response data from each postbaseline visit that occurs before discontinuation of treatment or addition of rescue medication through endpoint. The model will include the treatment group, visit, and interaction between treatment group and visit. An unstructured covariance structure will be used for the repeated measures. If the model fails to converge with the unstructured covariance structure, the heterogeneous Toeplitz structure or further reduced covariance structure may be used instead. The odds ratio for the treatment difference, 95% CIs for the odds ratio, and p-value will be provided.

Abbreviations: CI = confidence interval, EQ-5D-5L = EuroQol 5 Dimension 5 Level, mITT = modified intent-to-treat, MDS-UPDRS = Movement Disorder Society – Unified Parkinson’s Disease Rating Scale, LSMean = least squares mean, mITT = modified intent to treat, MMRM = Mixed Model for Repeated Measures, PDQ-39 = 39-Item Parkinson’s Disease Questionnaire, VAS = visual analog scale.

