3. KEY ASSESSMENTS AND DERIVATIONS

3.1. Efficacy Assessments

3.1.1. Hauser Diary

The Hauser diary assesses patient-defined motor function status over a period and provides a tool for assessment of change in “off” time and “on” time with troublesome dyskinesia ([Hauser et al, 2000](#)). The Hauser diary asks patients to rate their mobility for each 30 minute period and to record their status for the majority of the period in 1 of 5 categories as: “on” time without dyskinesia, “on” time with non-troublesome dyskinesia, “on” time with troublesome dyskinesia, “off” time, or asleep.

Subjects will record diary entries at home at 30 minute intervals for 24 hours on 2 consecutive days within the 7 days before randomization at the Baseline Visit and at 30 minute intervals for 24 hours on 2 consecutive days within the 7 days before each postbaseline clinic visit.

Valid Hauser diaries should contain no more than 2 hours (four 30-minute periods) of missing entries total per 24 hours diary. If a diary contains more than 2 hours of missing data, it will not be considered valid. Valid diaries of the 2 days prior to a given visit should be averaged for the parameters needed for analysis.

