3.1.1.3. Handling Missing Hauser Diary Entries

If less than 2 valid diaries are returned by the subject for a given visit, the following method for calculating the average parameters will be followed:

- If only 1 of the daily diaries is valid then it will be used to calculate the average parameters
- If there are no valid subject diaries for a particular visit, then the data will be considered missing for that visit

In the case of a missing entry in a specific 30-minute time slot for a valid Hauser diary day (i.e. less than 2 hours missing per day), the missing slot will be imputed by carrying forward the value of the last 30-minute epoch prior to time slot of the missing value (a last observation carried forward (LOCF) approach) unless the previous 30-minute slot is on the prior day. In the case when the LOCF is not feasible (either the prior slot is also missing or the prior slot is not on the same day), the entry of the time next slot will then be carried backward (NOCB) to impute the missing slot. In the unlikely event of 2 or 3 consecutive missing time slots on a day with valid day of Hauser diary, the approach will be applied consecutively to fill the missing slots.

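### The diary-defined mITT set is also used for MDS-UPDRS, PDQ-39 and EQ-5D-5L, so a subject with usable scale scores but no valid post-baseline diary could be left out

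*SAP*

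**What the plan says.** SAP 5.2 Table 4 makes mITT the primary efficacy set. Besides randomisation and one dose, a subject must "have both a valid baseline and at least 1 postbaseline valid Hauser diary entry". There is no condition on any other instrument. Protocol 9.3 Table 8 has the same structure without the validity requirement: subjects must "have both a baseline and at least 1 postbaseline Hauser diary entry".

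Validity is defined in SAP 3.1.1: "If a diary contains more than 2 hours of missing data, it will not be considered valid". SAP 3.1.1.3 adds that one good day of the two is sufficient: "If only 1 of the daily diaries is valid then it will be used to calculate the average parameters".

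The table in SAP 5.12 names mITT, the hypothetical strategy and the MMRM of SAP 5.9.2 for every row. The rows not based on the diary are MDS-UPDRS Parts I, II and III (for example, the row beginning "Change from baseline in the MDS UPDRS Part II score (all time points"), "Change from baseline in the PDQ 39 score", "Change from baseline in the EQ-5D-5L index score" and the EQ-5D-5L VAS. SAP 5.13 explores MDS-UPDRS Part II+III by the same method and appears to inherit the set. Protocol 9.4.1 Table 9 is consistent with this but does not name the set for the scales: "Continuous secondary and other endpoints (MDS-UPDRS, EQ-5D-5L index and VAS scores and PDQ-39 score) will be analyzed in a manner similar" to the primary and key secondary endpoints.

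**The concern.** The diary condition makes sense for the two diary endpoints: a subject with no valid post-baseline diary has nothing to contribute. It has no such function for a rating scale or questionnaire. There it removes subjects for failing a different instrument, although their scale scores have been collected.

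Membership depends on behaviour after randomisation, so the excluded subjects are unlikely to be a random subset. They would mostly be early leavers and people who persistently fail to complete the diary. Protocol 2.3 reports dose-dependent nausea and lists adverse events that led to stopping tavapadon, so early leaving could differ between arms. At stake are a little precision and some representativeness in the supportive scale results.

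**Working it through.** **1. The plan's own figure.** The documents size only the diary endpoint. Inputs from SAP 1.2: difference 1 h, SD 2.5, two-sided alpha 0.049, power 90%, dropout 27%.

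- Normal approximation: n per arm = 2 × 2.5² × (1.969 + 1.282)² / 1² = 12.5 × 10.57 = 132.1, so 133; 133/0.73 = 182.2, so 183.
- Exact noncentral t: 134 per arm; 134/0.73 = 183.6, so 184, as stated.
- Power with 135 completers per arm (270 in SAP 9.1.2.1 Table 5): 90.4% by noncentral t, as stated.

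The figure reproduces. It does not depend on which set is used for the scales.

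**2. Who is excluded.** Reading SAP 5.12 against Table 4, a dosed subject with a baseline and a post-baseline MDS-UPDRS score, but no post-baseline day with 2 h or less missing, is outside mITT and so outside every scale analysis. No other planned analysis picks the subject up. SAP 5.12 names no ITT or FAS run of the scales, and the missing-data sensitivity analyses of SAP 5.9.3 are extended only to the key secondary endpoint (SAP 5.10.3) and are themselves run within mITT.

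**3. How easily the diary condition is met.** By SAP Table 7, diaries are due at Weeks 2, 5, 8, 11, 14, 18, 22, 26 and 27. The first scheduled post-baseline score is at Week 5 for MDS-UPDRS (2 diary opportunities by then), Week 14 for EQ-5D-5L (5 opportunities) and Week 26 for PDQ-39 (8 opportunities). Let q be the probability that a visit yields no valid diary day. The value of q is assumed, as is independence between visits. The probability of failing at all of m visits is q^m:

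| m | q = 5% | q = 10% | q = 20% |
|---|---|---|---|
| 1 (one opportunity, early termination) | 5% | 10% | 20% |
| 2 (through Week 5) | 0.25% | 1% | 4% |
| 5 (through Week 14) | <0.001% | 0.001% | 0.032% |
| 8 (through Week 26) | <0.001% | <0.001% | <0.001% |

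For EQ-5D-5L and PDQ-39, exclusion is therefore almost confined to early-termination visits and persistent non-completers. Persistent non-completion breaks the independence assumption and would raise these figures.

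**4. What could be recovered.** The Week 27 assessments, which include all three scales, are done at premature discontinuation (SAP Table 7, footnote b). Under SAP 5.9.1, data after treatment discontinuation are censored, and SAP 5.12 applies that strategy to every row. Scores taken after stopping treatment are lost under any set. An early-termination visit on days 2 to 24 maps to Week 2 (SAP 4.2 Table 3), where no MDS-UPDRS is scheduled. The clear gain is on-treatment scores from Week 5 onward in subjects whose diaries were all invalid or missing.

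**5. Precision.** With k of 368 subjects excluded, the SE ratio is √(368/(368 − k)). The range of k is assumed.

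- k = 2 (2/368 = 0.5%): √(368/366) = 1.003
- k = 18 (18/368 = 4.9%): √(368/350) = 1.025

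This counts each excluded subject as fully informative and takes all 368 as contributing, so it suits early visits. Early leavers have no Week 26 value and add little to that contrast, where the plan expects about 270 completers.

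**The case against.** The strongest reply is that almost nobody will be affected. Concordance testing and a completed two-day diary are required before randomisation, so the baseline condition should rarely fail, and one valid day at any later visit satisfies the rest. This stands, and it limits the size of the point.

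A second reply is that a single prespecified efficacy set, essentially the same in protocol and SAP, gives one population across the efficacy tables. That is a real benefit. The SAP already departs from it for other instruments, though. SAP 5.15.2 and 5.15.3 run the SAP 5.9.2 MMRM on the ESS total score and the QUIP-RS total ICD score in the safety set, which has no diary condition.

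A third reply is that the alternative set also requires a post-baseline value and so is also a selection after randomisation. This is correct: the alternative is larger and tied to the right instrument, but it does not restore the full randomised comparison.

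A reader might also infer that the scale results will be biased between arms. The documents do not support that. Differential early leaving is plausible, but nothing in them shows that diary validity differs by arm.

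**Conclusion.** The mismatch is real on the text: the SAP makes inclusion in six scale analyses, and apparently in the exploratory Part II+III analysis, depend on a diary those analyses do not use. The effect is probably small. On the assumed range of 2 to 18 affected subjects, the cost is at most about 0.3% to 2.5% in standard error at early visits and less at Week 26. The Week 26 statement assumes that those affected are mainly early leavers. The direction and size of any bias cannot be derived from the documents.

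Two stronger readings should be resisted. One is that a known number of subjects is being dropped: exclusion is a consequence of the rule, and no count is given. The other is that the trial's main conclusions are at risk. The primary and key secondary endpoints are diary endpoints, for which the set is suitable, and SAP 5.4 treats the other secondary endpoints as supportive, tested at nominal level outside the controlled sequence. This is an inexpensive improvement and does not threaten the trial.

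**What to change.** Before unblinding, state in SAP 5.2, 5.12 and 5.13 that each non-diary endpoint is analysed in randomised, dosed subjects with a baseline and at least one post-baseline value of that endpoint, as randomised and under the same hypothetical strategy. Keep the diary-defined mITT for the diary endpoints and as a supportive set for the scales. Settling this before unblinding means the set cannot be chosen with results in view.

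The cost is one added definition in Table 4, changed set entries for six rows of SAP 5.12, a clarification in SAP 5.13, and a supportive run of each scale model. Subject counts will differ slightly between endpoint tables and need a footnote. The planned 368 subjects and the 90% power for the primary endpoint do not change.
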